18.6. Physical Examination

A listing of all physical examination assessments in subjects who had at least 1 abnormal physical examination finding will be provided.

18.7. Other Safety Assessments

18.7.1. Pulmonary Function Tests

The following pulmonary function test (PFT) measurements (actual and % Predicted) will be reported for this study:

- FEV₁
- FVC
- Total Lung Capacity (TLC)
- FEV₁/FVC ratio
- Forced Expiratory Flow (FEF) 25-75

- DLCO (if available)

The following summaries will be provided for PFT data:

- Value and change from Baseline by visit
- Incidence of markedly abnormal values by visit (Section 18.7.1.1)

All PFT data will be listed. A listing in subjects who ever reported an abnormality in PFT will also be provided, including a flag for whether markedly abnormal criterion is also met.

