6.3. Retests, Unscheduled Visits, and Early Termination Data

For by-visit analyses and summaries, efficacy, safety, HRQoL, and biomarker data (including scheduled, retests, unscheduled, and early termination) will be assigned to visits after the application of the windowing conventions described in Section 6.4. All measurements will be considered in summaries of abnormalities or worst-case values post-Baseline.

The visit windowing will be applied before missing data are imputed.

Listings will include scheduled, unscheduled, retest, and early termination data.

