6.4. Windowing Conventions

All scheduled study visits are defined relative to Study Day 1, the date of first dose. Scheduled visit windows are defined in Clinical Study Protocol APD334-301 Appendix 1. A windowing convention will be used to determine the analysis visit value for a given measurement and will be applicable for all by-visit summaries and analyses for efficacy and safety data. Refer to [Table 2](#) for specific visit windows.

Table 2: Visit Windows for Efficacy and Safety Analyses

For all efficacy (except endoscopy/MMS/histology), efficacy-related biomarkers, safety labs and vital signs	
Scheduled Study Visit (Protocol Scheduled Day)	Analysis Visit Window (Study Day)
Baseline	≤ 1
Week 0 (Day 1)	1
Week 0 (Day 2) ^a	2
Week 2 (Day 15 ± 3)	2 to 22, or 3 to 22 ^a
Week 4 (Day 29 ± 3)	23 to 43
Week 8 (Day 57 ± 3)	44 to 71
Week 12 (Day 85 ± 7)	72 to 99
Week 16 (Day 113 ± 7)	100 to 127
Week 20 (Day 141 ± 7)	128 to 155
Week 24 (Day 169 ± 7)	156 to 197
Week 32 (Day 225 ± 7)	198 to 253
Week 40 (Day 281 ± 7)	254 to 309
Week 48 (Day 337 ± 7)	310 to 351
Week 52 (Day 365 ± 14)	> 351
For endoscopy/MMS/histology/all composite endpoints that include an endoscopy component and/or RB/SF component, Physician’s Global Assessment, health-related quality of life, ECGs, OCT, and PFT	
Scheduled Study Visit (Protocol Scheduled Day)	Analysis Visit Window (Study Day)
Baseline	≤ 1
Week 0 (Day 1)	1
Week 0 (Day 2) ^a	2
Week 12 (Day 85 ± 7) ^{b,c}	66 to 113 (66 to 141 for assessments impacted by COVID-19 pandemic) ^d
Week 32 (Day 225 ± 7) [PFT only]	198 to 253 (198 to 281 for assessments impacted by COVID-19 pandemic) ^d
Week 52 (Day 365 ± 14) ^{b,d}	337 to 393 (337 to 421 for assessments impacted by COVID-19 pandemic) ^e

^a Applicable only for subjects who require extended monitoring on Day 2 for vital signs and ECGs.

^b Applicable to all Week 12 and Week 52 efficacy endpoints based on any component of Mayo clinic score, such as clinical remission and symptomatic remission. Protocol visit window for PFT and OCT at Week 12 is Day 85 ± 7 (FDA 2020).

^c Due to overlapping windows at Week 12 and Week 8/16, a hierarchical algorithm will be used for the mapping. Week 12 will always be mapped first, then assess records for the Week 8/16 mapping. If a scheduled Week 8 and 12, or Week 12 and 16 visits are both present in the same visit window, they will be mapped to separate visits (ie, Week 8 and Week 12 or Week 12 and Week 16).

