APPENDIX 1: PROGRAMMING CONVENTIONS FOR OUTPUTS

OUTPUT CONVENTIONS

Outputs will be presented as shown in the Output shells.

DECIMALS, PERCENTAGES, AND P-VALUES

- If the original data has N decimal places, then the summary statistics should have the following decimal places:
 - Minimum and maximum: N
 - Mean (and LS Means), median: N + 1
 - SD or SE: N + 2
- Percentages will be reported to one decimal place. Where counts are zero, percentages will not appear in the output.
- P-values will be reported to three decimal places, except values < 1.000 but > 0.999 will be presented as ' > 0.999 ' (eg, 0.9998 is presented as > 0.999).
- Values < 0.001 will be presented as ' < 0.001 ' (eg, 0.0009 is presented as < 0.001). Rounding will be applied after the < 0.001 and > 0.999 rule.

CONVENTIONS RELATED TO PHARMACOKINETIC DATA

All etrasimod concentrations will be reported and analyzed with the same precision as the source data provided by the bioanalytical laboratory regardless of how many significant figures or decimals the data carry. The derived PK data (etrasimod concentration) will be rounded to carry 3 significant digits and considered the source data for the calculation of descriptive statistics and the statistical analysis source data.

For the reporting of descriptive statistics, the mean, geometric mean, median, SD, % CV, and % geometric CV will be presented with 4 significant digits. The minimum and maximum will be presented with 3 significant digits.

DATES AND TIMES

Depending on data available, dates and times will take the form DDMMYYYY or DDMMYYYY:hh:mm.

SPELLING FORMAT

English US.

PRESENTATION OF TREATMENT GROUPS

For outputs, treatment groups will be represented as follows and in that order:

Treatment Group	For Tables, Graphs, and Listings
Etrasimod	Etrasimod
Placebo	Placebo
Screen Failure	Screen Failure
Not Treated ^a	Not Treated

^a To be used for subjects in safety listings who are randomized but do not receive study treatment.

PRESENTATION OF VISITS AND STUDY PERIOD

For outputs, visits and study periods will be represented as follows and in that order:

Visit Name	Study Period
Screening	Screening
Baseline, Day 1, Week 2, Week 4, Week 8, Week 12, Week 16, Week 20, Week 24, Week 32, Week 40, Week 48, and Week 52	Treatment
End of Study/Early Termination	Dependent on Analysis Visit assigned, described in Section 6.4
2-Week Follow-Up, 4-Week Follow-Up	Follow-Up

LISTINGS

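### Markedly abnormal lung function tests are counted only by visit, and the visit windows leave three stretches of treatment in which an early termination or unscheduled test has no row

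*SAP*

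**What the plan says.** SAP 18.7.1 lists two PFT summaries, and both are by visit. One is value and change from Baseline. The other is "Incidence of markedly abnormal values by visit (Section 18.7.1.1". Everything else in that section is a listing.

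SAP 6.4 says its windowing convention "will be applicable for all by-visit summaries and analyses for efficacy and safety data". Table 2 places PFT in the block that ends "health-related quality of life, ECGs, OCT, and PFT", not in the block for laboratory tests and vital signs. The windows that apply to PFT are:

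- Week 12: Days "66 to 113 (66 to 141 for assessments impacted by COVID-19 pandemic"
- Week 32 (PFT only): Days "198 to 253 (198 to 281 for assessments impacted by COVID-19 pandemic"
- Week 52: Days "337 to 393 (337 to 421 for assessments impacted by COVID-19 pandemic"

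The Day 2 row in the same block is footnoted to vital signs and ECGs. Unscheduled and early termination (ET) data can be allocated to an analysis visit, but SAP Appendix 1 gives ET no study period of its own; its entry reads "Dependent on Analysis Visit assigned, described in Section 6.4". Only the 2-Week and 4-Week Follow-Up visits are summarized without a window.

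SAP 6.3 adds a general rule: "All measurements will be considered in summaries of abnormalities or worst-case values post-Baseline".

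**The concern.** SAP 6.3 states an aim that SAP 18.7.1 gives no means of meeting for PFT. A test outside all three windows has no visit, and the only incidence table is organized by visit.

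Such tests are expected. Protocol 9.10.4 calls for a PFT at ET unless one was done in the preceding 4 weeks, and allows PFTs at unscheduled visits for respiratory adverse events. Protocol 5.1 requires treatment to stop when FEV1 and/or FVC falls below 50% of predicted. The same 50% cut-off defines two of the three markedly abnormal criteria in SAP 18.7.1.1. So a value that triggers the stopping rule on an unwindowed day is a value the incidence table was meant to count, and the plan as written does not count it.

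At stake is the by-arm frequency of a lung function finding in a drug class for which the SAP names airflow obstruction and reduced gas exchange as special-interest subcategories.

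**Working it through.** **1. Days with no PFT visit.** Inputs are the Table 2 windows, taken over Day 2 to Day 393, the end of the standard Week 52 window: 393 − 2 + 1 = 392 days.

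| Windows | Covered days | Uncovered stretches | Uncovered days |
|---|---|---|---|
| Standard | 48 + 56 + 57 = 161 | 2-65 (64), 114-197 (84), 254-336 (83) | 392 − 161 = 231 |
| COVID-19 extension applied to every assessment | 76 + 84 + 57 = 217 | 2-65 (64), 142-197 (56), 282-336 (55) | 392 − 217 = 175 |

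The stretches add up: 64 + 84 + 83 = 231 and 64 + 56 + 55 = 175. As shares of the calendar these are 231/392 = 58.9% and 175/392 = 44.6%. Tests after Day 393 (Day 421 with the extension) are also outside every window.

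**2. Control.** The laboratory and vital-sign block runs 2-22, 23-43, 44-71, 72-99, 100-127, 128-155, 156-197, 198-253, 254-309, 310-351 and above 351. It leaves no day uncovered, so the gap comes from the block in which PFT was placed.

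**3. Do tests that the protocol requires fall in the gaps?** Take a Week 12 PFT on its scheduled Day 85. The 4-week exemption for an ET PFT runs to Day 85 + 28 = 113, which is the last day of the standard Week 12 window. An ET PFT required from Day 114 to Day 197 then lies outside every standard window. For subjects with a history of mild pulmonary disease, who also have a Week 32 PFT on Day 225, the exemption runs to 225 + 28 = 253, again the last day of the window, and the next gap starts on Day 254.

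**4. Is there another row?** Reading the sections together:

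- SAP 18.7.1: by-visit incidence; no any-time, worst-value or end-of-treatment count.
- SAP 6.4: allocation only to a defined analysis visit.
- SAP Appendix 1: ET shown under whatever visit SAP 6.4 assigns.
- SAP 6.3: all measurements considered, but no row named.

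The SAP does provide such a count elsewhere. SAP 18.3.1 counts low lymphocytes and neutrophils at any time in the study, and SAP 18.4 has a shift to the worst post-Baseline ECG interpretation.

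**5. The second tier.** SAP 18.7.1.1 also defines potentially important values: a fall of more than 20% from Baseline in FEV1, FVC or DLCO. The incidence bullet names only markedly abnormal values, and so does the listing flag. DLCO has a criterion only in this second tier.

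**The case against.** The best defence is that SAP 6.3 already settles the matter. It first sends by-visit data to the windows, then says separately that all measurements count in summaries of abnormalities, and an incidence table of abnormal values is such a summary. Row layout is left to output shells that are not among these documents. This has force, and it is why the point should not be put as a flat contradiction. But SAP 6.3 names no row, and SAP 18.7.1, SAP 6.4 and Appendix 1 taken together supply none. A programmer holding a Day 150 value has nowhere to put it.

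Other objections stand in part:

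- **Follow-up.** A reader might infer that a subject stopped on Day 150 disappears from the table. That is not so. An earlier value can sit in the Week 12 row. Protocol 9.10.4 sends a subject below 50% of predicted to a follow-up visit, where a PFT is done if clinically indicated, and SAP 6.4 summarizes follow-up visits without a window. A lasting abnormality can appear there; the Day 150 value itself cannot.
- **Other outputs.** All PFT data are listed, with a separate flagged listing of subjects who ever had an abnormality. SAP 18.1.5 uses spirometry review to find special-interest cases and compares the arms. This covers part of the gap. A listing, however, gives no rate by arm, and the special-interest tables count adverse events, not PFT values.
- **By-visit format.** It is the SAP's usual format, and ECG and OCT share these windows. That explains the choice but does not close the gap.

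**Conclusion.** The point holds as a cheap improvement. As written, the plan leaves out-of-window ET and unscheduled PFTs out of its only PFT incidence table, so that table may undercount. No efficacy endpoint or test is touched, and no data are lost.

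The size is unknown. Three stronger readings are tempting, and the documents support none of them:

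- The share of uncovered days is not a share of missed tests. Week 12, 32 and 52 PFTs done on schedule all fall inside windows.
- The 50% dropout projected in SAP 16.1.4.1 cannot be turned into a number of missed ET tests. The documents do not say when subjects leave, and exits to the extension study open at Week 12, where the PFT is in window.
- Nothing shows that off-schedule PFTs are the likeliest to be abnormal. Symptom-triggered tests are at the investigator's discretion, and no rate of abnormal PFTs is given.

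The conclusion rests on reading the incidence bullet literally as by visit and on the absence of any unseen shell that adds an any-time row.

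**What to change.** Add one summary to SAP 18.7.1: the incidence of markedly abnormal values, and separately of potentially important values, at any time after Baseline, using every scheduled, unscheduled, ET and follow-up PFT regardless of window. Keep the by-visit table.

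State the denominators:

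- For the criteria on percent predicted: subjects with at least one post-Baseline PFT. No Baseline value is needed, because these criteria are absolute.
- For the criteria on a fall of more than 20%: subjects with a Baseline and at least one post-Baseline value of that measure.

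Extend the flag in the abnormality listing to the potentially important tier.

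The cost is one bullet, one extended flag and a few table rows; the data and criteria already exist. The drawback is that an any-time count rises with the number of tests, so arms with different follow-up or more unscheduled testing are not strictly comparable. The number of PFTs per arm should be printed beside it.

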18.7.1.1. PFT Markedly Abnormal and Potentially Important Criteria

Markedly abnormal quantitative PFT measurements will be identified in accordance with the following predefined markedly abnormal criteria:

- % Predicted FEV₁ < 50%
- % Predicted FVC < 50%
- % Predicted FEV₁/FVC ratio < 50%

Potentially important PFT measurements will also be identified using the criteria below:

- Decrease from Baseline > 20% in FEV₁, ie, percent change from Baseline < -20%
- Decrease from Baseline > 20% in FVC, ie, percent change from Baseline < -20%
- Decrease from Baseline > 20% in DLCO, ie, percent change from Baseline < -20%

18.7.2. Ophthalmoscopy and Optical Coherence Tomography

The following summaries will be provided for ophthalmoscopy and optical coherence tomography (OCT) data:

- Values and change from Baseline in central foveal thickness and intraocular pressure by visit
- Categorical result in ophthalmoscopy with OCT parameters by visit (the categories are listed on the eCRF)

Only PFT and OCT assessments completed by 50 or more subjects in the Safety Set will be presented in the summaries.

A listing of all ophthalmoscopy and OCT assessments will be provided. A listing of subjects who ever reported an abnormality in OCT will also be provided. Additionally, a listing of retinal photograph and eye pressure assessments will be provided for subjects who experienced an AE related to eye disorders.

18.7.3. Tuberculosis Screening and Chest X-Ray

Screening TB results and chest X-rays will be listed. Results of TB questionnaires will also be listed.

19. EFFICACY-RELATED BIOMARKERS

Value and change from Baseline in level of FCP, hs-CRP, and lymphocyte counts at protocol-specified visits will be summarized by visit and treatment for the FAS with Baseline MMS 5 to 9. Additionally, percent change from Baseline in lymphocyte counts will also be summarized. Change from Baseline in these biomarkers will also be analyzed using an MMRM, with factors for naïve to biologic or JAK inhibitor therapy at study entry (Yes or No), Baseline corticosteroid use (Yes or No), Baseline disease activity (MMS: 4 to 6 or 7 to 9), treatment, visit, treatment by visit interaction, a covariate of the corresponding Baseline value, and a random subject effect. Reported randomization stratum will be used in the model. Unstructured covariance will be used. If there is a convergence issue in fitting the unstructured covariance, a compound symmetry covariance structure will be used. The same model will be fit to the percent change from Baseline in lymphocytes. LS means, SEs, CIs, and p-values by visit will be reported.

Additionally, the following summaries will be provided for biomarker data:

- Line plots over time for LS mean and SE for the following laboratory assessments:
 - Change from Baseline in lymphocytes
 - Percent change from Baseline in lymphocytes
 - Change from Baseline in hs-CRP
 - Change from Baseline in FCP

The exploratory efficacy-related biomarker analyses for immunophenotyping, proteomics, RNA transcriptomics, and fecal microbiome will be described in a separate biomarker analysis plan.

20. PHARMACOKINETICS

Plasma concentrations of etrasimod, and if warranted M3 (AR503641) and M6 (AR504344) will be assessed from PK samples collected prior to dosing and 4 hours (\pm 15 minutes) postdose (after 12-lead ECG) on Week 0/Day 1. Additionally, PK samples will be collected prior to dosing (trough) at Weeks 2, 4, 8, 12, 16, 20, 24, 32, 40, 48, and 52, and for PK samples collected at the 2-Week and 4-Week Follow-Up visits for subjects not enrolled into any extension study. Concentrations below the limit of quantitation (BLQ) will be assigned a numerical value of zero for the calculation of descriptive statistics. For geometric mean and geometric % coefficient of variation [CV], the zero values will be excluded.

The pharmacokineticist will determine the strategy for dealing with data affected by protocol deviations or events which may impact the quality of etrasimod concentration data on a case-by-case basis with input from the Arena study physician and Arena clinical pharmacologist, as needed. Examples for protocol deviations or events include, but may not be limited to, vomiting within 4 hours after etrasimod dose administration on Week 0/Day 1 or on the day prior to trough sample collection, sample processing errors that lead to inaccurate bioanalytical results, and/or inaccurate dosing prior to PK sampling. In the case of an important protocol deviation or event, the affected PK data collected may be excluded from the summaries, calculation of the

average steady-state trough plasma concentration ($C_{\text{trough,ss}}$) based on Week 2 to Week 52 trough concentrations ($C_{\text{trough,ss,W2-W52}}$), exposure-response analysis, and/or population PK analysis, but will still be reported in the study result listings.

Unless otherwise specified, PK summaries will use the Pharmacokinetic Set. Exposure-response analysis will use the Safety Set.

Individual subject etrasimod plasma concentrations (and etrasimod metabolite concentrations, if applicable) will be presented in the data listings, including subject ID, treatment received, sex, age, weight, tobacco use, nominal timepoint, actual blood collection date/time, concentration, and time since last dose and also summarized using descriptive statistics (n, mean, SD, % CV, geometric mean, geometric % CV, median, minimum, and maximum) by nominal timepoint.

All subjects are expected to achieve steady-state plasma concentration by Week 2. For each subject, the average steady-state trough (predose) plasma concentration based on Week 2 to Week 52 trough concentrations ($C_{\text{trough,ss,W2-W52}}$) per subject will also be calculated and presented in a data listing and summarized using descriptive statistics.

Mean (\pm SD) etrasimod concentration versus nominal time (Weeks 0 to 52) will be plotted on linear scales. Additionally, a mean (\pm SD) concentration-time plot with etrasimod and metabolites overlaid on linear and semi-logarithmic scale will be generated.

Box plots of etrasimod, M3, and M6 concentrations at Day 1, 4-hour postdose timepoint (C_{4h}), steady-state C_{trough} (Weeks 2 through 52), and $C_{\text{trough,ss,W2-W52}}$ will be plotted versus nominal timepoint on ordinal scale.

Individual subject plasma concentrations versus actual time (Weeks 0 to 52) will be plotted since start of treatment on linear and semi-logarithmic scales. Individual subject plots with etrasimod and metabolite concentration data will be overlaid on the same plot.

Scatter plots of individual subject average steady-state $C_{\text{trough,ss,W2-W52}}$ versus Baseline body weight and versus Baseline age (age at consent) as continuous variables will be generated for the Pharmacokinetic Set, which will also include the Spearman's rank correlation coefficient, p-value, and locally estimated scatterplot smoothing (LOESS) trend line.

To explore potential etrasimod plasma exposure-response relationships, the following scatter plots will be generated for the Safety Set, including data from placebo subjects (plotted at 'zero' concentration). Any contributing data from the placebo subjects will be annotated with a different color or symbol. All scatter plots will include the Spearman's rank correlation coefficient, p-value, and LOESS trend line (based on subjects that received active treatment only).

- Individual subject absolute change from Baseline in MMS versus etrasimod steady-state C_{trough} at Week 12
- Individual subject absolute change from Baseline in MMS versus etrasimod steady-state C_{trough} at Week 52
- Individual subject lymphocytes versus etrasimod steady-state C_{trough} at Week 52 and grouped all visits (Weeks 2 through 52 pooled)

- Individual subject absolute changes from Baseline in lymphocytes versus etrasimod steady-state C_{trough} at Week 52 and grouped all visits (Weeks 2 through 52 pooled)
- Individual subject percent changes from Baseline in lymphocytes versus etrasimod steady-state C_{trough} at Week 52 and grouped all visits (Weeks 2 through 52 pooled)
- Individual subject heart rate versus etrasimod concentration at matching visit/timepoint for Week 0/Day 1; the 4-hour postdose vital results will be presented on the left panel and safety ECG on the right panel.
- Individual subject absolute changes from Day 1 Predose in heart rate versus etrasimod concentration at matching visit/timepoint for Week 0/Day 1; the 4-hour postdose vital results will be presented on the left panel and safety ECG on the right panel.

Furthermore, the following overlay plots will be generated for the Pharmacokinetic Set within the etrasimod group only:

- Mean (SD) absolute lymphocyte counts and mean (SD) etrasimod concentration versus nominal timepoint (Weeks 0 through 52)
- Mean (SD) absolute change from Baseline in lymphocytes and mean (SD) etrasimod concentration versus nominal timepoint (Weeks 0 through 52)
- Mean (SD) percent change from Baseline in lymphocytes and mean (SD) etrasimod concentration versus nominal timepoint (Weeks 0 through 52)
- Mean (SD) heart rate and mean (SD) etrasimod concentration versus nominal timepoint (Weeks 0 through 52)
- Mean (SD) absolute change from Baseline in heart rate and mean (SD) etrasimod concentration versus nominal timepoint (Weeks 0 through 52)

All summary figures for etrasimod plasma concentrations and for change from Baseline in MMS versus etrasimod steady-state C_{trough} will be repeated by:

- Sex (Male or Female)
- Weight (\leq Median or $>$ Median)
- Age group (< 18 , 18 to < 65 , or ≥ 65 years)
- Tobacco use (Yes or No)

The plasma concentrations over time will be used in a population PK analysis, which will be described in a separate plan.

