10.9.3. Biomarkers

- Change from baseline in level of fecal calprotectin at Weeks 2, 4, 8, 12, 24, and 52
- Change from baseline in level of hs-CRP at Weeks 2, 4, 8, 12, 16, 20, 24, 32, 40, 48, and 52
- Change and percentage change from baseline in lymphocyte counts at Weeks 2, 4, 8, 12, 16, 20, 24, 32, 40, 48, and 52

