6.5. Statistical Tests

The default significance level will be 0.05; confidence intervals (CIs) will be 95%, and all tests will be 2-sided, unless otherwise specified in the description of the analyses.

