7. DETERMINATION OF SAMPLE SIZE

Based on a 2-group Fisher’s exact test, a 1-sided significance level of 0.025, and a 2:1 randomization ratio, 420 total subjects (280 etrasimod, 140 placebo) are required to achieve 93.4% power to detect a difference of 13.5% in the primary endpoint of clinical remission at Week 52 between the etrasimod treatment group (23.5%) and the placebo treatment group (10.0%). With this sample size, there will be 96% power to detect a difference of 12.5% in the other primary endpoint of clinical remission at Week 12, assuming a placebo rate at 6.0%. The lower bound of overall power for both primary endpoints (as coprimary endpoints), is at least 90%; since the 2 primary endpoints are expected to be at least moderately, positively correlated, the actual overall power to reject both of their null hypotheses is likely to be greater than 90%. Workbook calculations from EAST® 6 statistical software are included below.

Design: Discrete Endpoint: Two-Sample Test - Parallel Design - Fisher's Exact

Test Parameters	
Design ID	Week 52 Clin Rem
Test Type	2-Sided
Specified α	0.05
Power	0.934
Sample Size (n)	420
Model Parameters	
Proportion Treatment (π_t)	0.235
Proportion Control (π_c)	0.1
$\delta = \pi_t - \pi_c$	
Under H0	0
Under H1	0.135
Allocation Ratio (n_t/n_c)	2

Sample Size Information

Sample Size (n)	420
Treatment (n _t)	280
Control (n _c)	140

Design: Discrete Endpoint: Two-Sample Test - Parallel Design - Fisher's Exact

Test Parameters	
Design ID	Week 12 Clin Rem
Test Type	2-Sided
Specified α	0.05
Power	0.96
Sample Size (n)	420
Model Parameters	
Proportion Treatment (π_t)	0.185
Proportion Control (π_c)	0.06
$\delta = \pi_t - \pi_c$	
Under H0	0
Under H1	0.125
Allocation Ratio (n_t/n_c)	2

⊖ **Sample Size Information**

Sample Size (n)	420
Treatment (n _t)	280
Control (n _c)	140

8. STATISTICAL CONSIDERATIONS**8.1. Multicenter Studies**

This study will be conducted by multiple investigators at multiple centers internationally. Randomization to treatment groups is stratified by:

- Naïve to biologic or JAK inhibitor therapy at study entry (Yes or No)
- Baseline corticosteroid use (Yes or No)
- Baseline disease activity (MMS: 4 to 6 or 7 to 9)

Data from all sites will be pooled and statistical analyses will not be adjusted for investigational site, country, or geographic region.

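### Three pooled lymphocyte exposure-response plots in SAP Section 20 carry a Spearman p-value with no allowance for up to 11 correlated pairs per subject

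*SAP*

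**What the plan says.** SAP Section 20 introduces a set of scatter plots on the Safety Set to explore exposure-response. Every one is to carry a Spearman "rank correlation coefficient, p-value, and LOESS trend line (based on subjects that received active treatment only").

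The first lymphocyte plot is listed as "Individual subject lymphocytes versus etrasimod steady-state C_{trough} at Week 52 and grouped all visits (Weeks 2 through 52 pooled"). The absolute-change plot is likewise given at Week 52 and "grouped all visits (Weeks 2 through 52 pooled"), and the percent-change plot reads "Individual subject percent changes from Baseline in lymphocytes versus etrasimod steady-state C_{trough} at Week 52 and grouped all visits (Weeks 2 through 52 pooled"). Each of the three therefore has an unpooled Week 52 version and a pooled version.

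The two variables are measured at the same visits. For exposure, "PK samples will be collected prior to dosing (trough) at Weeks 2, 4, 8, 12, 16, 20, 24, 32, 40, 48, and 52". For lymphocytes, Protocol Section 10.9.3 lists "Change and percentage change from baseline in lymphocyte counts at Weeks 2, 4, 8, 12, 16, 20, 24, 32, 40, 48, and 52".

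Section 20 does not say how the p-value on a pooled plot is computed. It mentions no clustering adjustment, per-subject summary or resampling for these plots, and it does not label the p-value as descriptive only.

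**The concern.** The standard Spearman p-value treats every plotted point as an independent observation. Repeated troughs from one person on a fixed daily dose tend to resemble each other, and so do repeated lymphocyte counts. When both do, the pooled points carry less information than their number suggests, and the p-value comes out too small. A named test with no stated modification will most likely be programmed in its default form.

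At stake is the accuracy of three printed p-values. A reader of the study report could take a weak or absent within-arm relation between trough and lymphocytes as established.

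The SAP avoids this problem elsewhere. Section 19 analyses lymphocyte change with a repeated-measures model. In Section 20 itself, the plots against body weight and age use one average trough per subject.

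**Working it through.** The documents state no figure for this point, so there is none to reproduce.

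**Inputs from the documents**
- Active-treated subjects: n = 280 (SAP Section 7: "420 total subjects (280 etrasimod, 140 placebo) are required").
- Visits with both measurements, Weeks 2 to 52: m = 11 (SAP Section 20; Protocol Section 10.9.3).
- Significance level: 0.05 by default, and "all tests will be 2-sided, unless otherwise specified in the description of the analyses" (SAP Section 6.5).
- Projected overall dropout: 50% (SAP Section 16.1.4.1).

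**Assumed, because the documents do not give them**
- Within-subject correlations ICC_x (trough) and ICC_y (lymphocytes), equal between all pairs of visits and varied from 0 to 0.8.
- Only active-treated subjects enter the coefficient.
- For the dropout case, half the subjects stop at a uniformly distributed point after the fourth visit.

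**Step 1. Number of pairs.** 280 x 11 = 3,080 at most.

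**Step 2. Variance inflation.** With no true association, the variance of the pooled coefficient is inflated by about D = 1 + (m - 1) x ICC_x x ICC_y = 1 + 10 x ICC_x x ICC_y. If either correlation is zero, there is no inflation. The equivalent number of independent pairs is 3,080 / D. The approximate type I error is the two-sided normal tail probability beyond 1.96 / sqrt(D).

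**Step 3. Simulation.** The ordinary pooled Spearman test was run on 2,000 data sets per setting with no association.

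| ICC in both | D | Equivalent pairs | Type I, formula | Type I, simulated, 11 visits | Type I, simulated, 50% dropout (about 2,520 pairs) |
|---|---|---|---|---|---|
| 0 | 1.0 | 3,080 | 5.0% | 5.2% | 4.8% |
| 0.2 | 1.4 | 2,200 | 9.8% | 9.6% | 9.1% |
| 0.3 | 1.9 | 1,621 | 15.5% | 13.6% | 12.6% |
| 0.5 | 3.5 | 880 | 29.5% | 27.0% | 26.2% |
| 0.7 | 5.9 | 522 | 42.0% | 42.2% | 36.9% |
| 0.8 | 7.4 | 416 | 47.1% | 46.6% | 42.8% |

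The simulation standard error is sqrt(p(1 - p)/2,000), about 0.5 percentage points at 5% and 1.1 at 47%. With unequal correlations of 0.5 and 0.3, D = 1 + 10 x 0.15 = 2.5 and the simulated error is 21.4%.

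**Step 4. What a reader would see.** Take a pooled coefficient of 0.05 on 3,080 pairs. Naively, z = 0.05 x sqrt(3,079) = 2.77 and p = 0.006. Dividing z by sqrt(D):
- ICCs of 0.3: 2.77 / sqrt(1.9) = 2.01, p about 0.04.
- ICCs of 0.5: 2.77 / sqrt(3.5) = 1.48, p about 0.14.
- ICCs of 0.7: 2.77 / sqrt(5.9) = 1.14, p about 0.25.

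**Step 5. One pair per subject.** On the same simulated data, Spearman on subject-mean trough against subject-mean lymphocytes rejected 4.2% to 5.9% of the time across all settings, which is nominal within simulation error.

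**The case against.** Four points can be made for the plan as written.

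- **The SAP nowhere says that the pooled points are treated as independent.** That is so. The default test is inferred from silence, and a programmer could choose a clustered method. But nothing in Section 20 asks for one, so the plan at least leaves room for an invalid p-value.
- **The size is unknown.** This also stands. At correlations of 0.2 to 0.3 the inflation is moderate, with D below 2. Calling the p-values grossly too small would require correlations of about 0.5 or more in both variables, which the documents neither give nor rule out.
- **The plots are exploratory.** They feed no primary or key secondary test and play no part in the multiplicity procedure of SAP Section 8.4. The lymphocyte treatment comparison rests on the model in Section 19, and population PK goes to a separate plan. This limits the importance of the point but does not make the printed p-value correct.
- **A true null may be implausible.** Protocol Section 1.3 already reports a dose-dependent fall in lymphocytes. Whether trough variation among subjects all taking 2 mg tracks lymphocytes is a narrower question, and it is the one these plots address.

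A reader might infer that all the exposure-response p-values are affected. The documents do not support that. The MMS plots (Week 12, Week 52), the Week 52 lymphocyte plots and the Day 1 heart-rate plots each use one visit or timepoint.

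**Conclusion.** The point holds for the three pooled lymphocyte plots only, and it is minor. If the ordinary Spearman p-value is printed there, it is too small whenever trough and lymphocytes are both positively correlated within subject. Over assumed correlations of 0.2 to 0.8, the nominal 5% test rejects a true null about 10% to 47% of the time with all visits present, and about 9% to 43% under the assumed 50% dropout. These figures rest on equal correlation between visits and on active-treated subjects only.

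The second assumption needs confirming. Placebo subjects are plotted at zero concentration, and the active-only restriction in Section 20 could be read as governing just the LOESS line. If placebo subjects entered the coefficient, it would also reflect the difference between arms.

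It would be wrong to conclude that any efficacy or confirmatory result is in doubt. No such result uses these p-values.

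**What to change.** Keep the three pooled scatter plots for display, and state in SAP Section 20 that the ordinary Spearman p-value will not be printed on them. Then choose one of the following:

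- Show the pooled coefficient without a p-value.
- Take coefficient and p-value from one pair per active-treated subject: C_trough,ss,W2-W52, which the SAP already derives, against that subject's mean lymphocyte value, change or percent change over the same visits.
- Keep the pooled coefficient and obtain its p-value or interval by a bootstrap or permutation that resamples whole subjects.

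In the same edit, say that the coefficient as well as the LOESS line uses active-treated subjects only, if that is the intention.

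The cost is small but not zero. The SAP defines no per-subject lymphocyte means, so three simple derivations are needed for the one-pair version. That version also drops the within-subject variation shown on the pooled plot, and it averages over different visits for subjects who stop early. No new data are needed, and no primary or key secondary analysis changes.
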